If you are creating a new protocol, select "I am submitting a new protocol." As 5 Year Renewals are no longer required, this option remains for historical purposes.
I am submitting a new protocol

Division & Personnel

Division

What Division/Department does the PI belong to?

Substance Use

Within the division/department, what Center or group are you affiliated with, if any?

STARS

Unaffiliated Personnel

List investigators, if any, who will be participating in this protocol but are not affiliated with New York State Psychiatric Institute or Columbia University. Provide: Full Name, Degrees and Affiliation.

This project is a single-site trial.

Procedures

To create the protocol summary form, first indicate if this research will include any of the following procedures

- Psychiatric Assessment
- Collection of Biological Specimens
- Medication Trial
- Use of Investigational Drug or Device
- Internet-based Data Collection or Transmission

Population

Indicate which of the following populations will be included in this research

- Medically and Psychiatrically Healthy Subjects
- Adults
- Adults over 50
- Substance Users

Research Support/Funding

Will an existing internal account be used to support the project?

Yes

Describe internal account

U54DA037842-01 Shared Pharmacotherapeutic Strategies for Cannabinoid & Opioid Use Disorders

Is the project externally funded or is external funding planned?

Yes

Select the number of external sources of funding that will be applicable to this study

Funding Source #1

Is the PI of the grant/contract the same as the PI of the IRB protocol?

Yes

Select one of the following

The grant/contract is currently funded

Source of Funding

Federal

Institute/Agency

NIDA

Grant Name

Shared Pharmacotherapeutic Strategies for Cannabinoid & Opioid Use Disorders

Grant Number

U54DA037842-01

Select one of the following

Single Site
Business Office
RFMH

Does the grant/contract involve a subcontract?

Yes
Subcontracted?
To
Name institution(s)

Columbia University

Study Location

Indicate if the research is/will be conducted at any of the following

- NYSPI**
- Other Columbia University Medical Center Facilities**

This protocol describes research conducted by the PI at other facilities/locations

Yes

- Hospital, clinics and other healthcare facilities**

Hospitals, clinics and other healthcare facilities

Select from the list

or type in location(s)..

STARS

Lay Summary of Proposed Research

Lay Summary of Proposed Research

The proposed study is a 12-week, open-label pilot study of sublocade (extended-release buprenorphine, BXR) as treatment for opiate use disorder (OUD) testing positive for Highly Potent Synthetic Opioids (HPSO). We plan to enroll 10 participants into the study. Outpatients seeking treatment for OUD will be screened, and those eligible and consenting will be inducted onto sublingual buprenorphine (target dose 16mg to 24mg). On the fourth day after starting the buprenorphine induction, participants will receive BXR 300mg by subcutaneous injection. Participants will be seen twice per week for urine collection for toxicology and research assessments and will have Medication Management counseling weekly during one of these visits. BXR will be administered monthly and dosing will be according to the FDA prescribing instructions of 300mg for the second dose and 100mg for the third. The aim of this study is to determine if BXR injection using standard dosing is a feasible treatment for patients with OUD who are positive for HPSO.

Background, Significance and Rationale

Background, Significance and Rationale

The US opioid epidemic continues to evolve with high-potency synthetic opioids (HPSO) now driving higher overdose fatality rates. There has been a five-fold increase in the US HPSO fatal overdose rate from 2013 (3,105) to 2016 (approximately 20,000) out of the approximately 42,000 overdose deaths due to opioids. Fentanyl analogs and other high-potency synthetic opioids (e.g., U-47700) are now commonly found in heroin and counterfeit prescription painkiller pills. In New York City, approximately one-half of all overdose deaths in 2017 involved fentanyl analogues. The high potency (e.g., carfentanyl is 10,000 times more potent than morphine) of these agents presents a new challenge for clinical treatment. Due to the rapidly changing nature of the illicit drug supply, the effectiveness of commonly used pharmacotherapies for opioid use disorder (OUD) (e.g., buprenorphine, methadone, naltrexone) in treating users of high-potency synthetic opioids is unknown. Experience at our research clinic in New York City is that nearly 80% of patients self-reporting heroin use are positive for fentanyl analogs, typically without their knowledge. Our experience with an ongoing clinical trial utilizing buprenorphine and extended-release injectable naltrexone is that the use of these treatments is more problematic in patients with OUD who test positive for fentanyl analogues, and our success rates are lower than compared to our own historical clinical trial controls. The increasing number of overdose deaths combined with lower efficacy of standard therapies creates an urgent need to develop new strategies for the HPSO using patient.

Despite the known effectiveness of buprenorphine sublingual (BSL) maintenance treatment, retention and continued non-prescribed opioid use remain significant limitations. Two recent large trials comparing BSL to other OUD pharmacotherapies found that around 50% or more of patients treated with BSL dropped out of treatment by 3 to 6 months. The first long-acting injectable buprenorphine (Sublocade™) became commercially available in 2018 after receiving an FDA Fast Track and Priority Review designation. This monthly buprenorphine formulation, which is available in two doses (100 mg and 300 mg), can achieve serum buprenorphine concentrations in excess of that achieved by BSL 24 mg per day. Moreover, if an unexpected drug holiday is experienced, at two weeks past the injection due date, μ -opioid receptor remains above 70%, providing some measure of protection against relapse to opioid use. While the Sublocade™ buprenorphine extended-release (BXR) injection product has not yet been compared to BSL treatment for the treatment of OUD, the pharmacologic advantages of BXR can be expected to improve treatment retention and outcome. The extended-release injection aspect should improve compliance and reduce relapse by providing more continuous buprenorphine serum levels as compared to the sublingual formulation. We hypothesize that the BXR injection will have particular benefit for individuals using fentanyl analogues and other HPSO because by providing continuous therapeutic serum buprenorphine levels there will be substantially less opportunity for non-compliance and relapse. Even in the case of a delayed injection, therapeutic levels of buprenorphine will be present for up to two weeks.

We propose an open-label, uncontrolled pilot study, in which patients seeking treatment for OUD who are positive for fentanyl analogues at screening (N = 10) will be inducted onto BSL and then receive BXR injection, with a primary outcome comparison of end of study opioid use compared to baseline. To our knowledge, this would be the first trial to examine the use of this BXR injection formulation for the treatment of OUD patients positive for fentanyl analogues, and the first pharmacotherapy trial of any agent for the treatment of patients with OUD testing positive for HPSO.

Specific Aims and Hypotheses

Specific Aims and Hypotheses

Aim 1: To determine if BXR injection using standard dosing is a feasible treatment for patients with OUD who are positive for HPSO.

Primary Hypothesis: BXR treatment will be associated with decreased opioid use for OUD patients positive for HPSO. The primary outcome measure will be opioid use during the last two weeks of the study compared to baseline as measured by a combination of urine toxicology and self-report.

Secondary Hypotheses: BXR injection will be associated with reduce symptoms of craving and symptoms of withdrawal as compared to baseline.

If found promising, the results of this pilot trial would support advancement of conducting a controlled trial, with the potential to improve the effectiveness of OUD pharmacotherapy for this subgroup more vulnerable to fatal overdose.

Description of Subject Population

Sample #1

Specify subject population

Adults with OUD testing positive for HPSO

Number of completers required to accomplish study aims

5

Projected number of subjects who will be enrolled to obtain required number of completers

10

Age range of subject population

18-65

Gender, Racial and Ethnic Breakdown

We plan to enroll 10 participants into the study. Both males and females will be recruited. All eligible participants are accepted; however, past experience with recruitment for opioid use disorders suggests that the approximate gender distribution for this study will likely be 20% female and 80% male. Previous and ongoing opiate studies at STARS have had samples comprised of approximately 50% Caucasians, and 50% ethnic minorities distributed as 24% African-American and 22% Hispanic-American, and 4% other. We anticipate a similar representation in this project. We will make every effort to recruit minority patients in order to ensure the generalizability of our findings to the overall treatment population.

Description of subject population

Prospective subjects will be 10 men or non-pregnant women of any ethnicity or race, aged 18-65. Enrolled

subjects will be individuals with OUD who test positive for HPSO.

Recruitment Procedures

Describe settings where recruitment will occur

The project will be completed at the Substance Treatment and Research Services (STARS downtown) situated on [name].

How and by whom will subjects be approached and/or recruited?

Screening for this study will be covered by the Substance Treatment and Research Service (STARS) umbrella screening protocol #6582R (PI: [name]). Trained research assistants and administrative assistants under the supervision of the principal investigator conduct the initial phone screening. Under protocol #6582R, patients who contact STARS interested in research trial participation are informed that they will be asked questions of a personal nature and asked to provide verbal consent for such questions. A "phone screen" form is completed by the phone screener, which asks basic demographic information, contact information (for scheduling purposes) and description of substance use to determine whether an in-person evaluation appointment is appropriate. Individuals are also informed that if they make an initial screening appointment this "phone screen" information will be forwarded to the clinician to facilitate the first meeting.

All patients will receive an explanation of the study risks, benefits, treatments, procedures, and option for alternative treatments. Patients who wish to participate will be asked to sign the treatment consent form following resolution of any questions and clear indication that they understand the nature of the study and consent form.

How will the study be advertised/publicized?

We will recruit individuals with OUD through newspapers, radio and public service announcements coordinated by the NYSPI Public Relations Office. This method has proven successful in several clinical trials at STARS. All advertisements will be sent to the Institutional Review Board for approval. The first phase of recruitment is a structured telephone interview when the initial contact is made. Individuals interested in receiving treatment for OUD will be asked to come to STARS for additional screening as per protocol #6582R. Those patients who meet criteria for OUD and all other inclusion/exclusion criteria will be asked if they are interested in participating in the study.

Do you have ads/recruitment material requiring review at this time?

No

Does this study involve a clinical trial?

Yes

YOU MUST REGISTER AT ClinicalTrials.gov IMMEDIATELY UPON RECEIPT OF IRB APPROVAL AND PRIOR TO ENROLLMENT OF THE FIRST SUBJECT. YOU WILL BE PROVIDED WITH A NCT REGISTRATION NUMBER ON REGISTRATION. PLEASE REVISE THIS SECTION OF THE PROTOCOL SUMMARY FORM TO INCLUDE THE NCT NUMBER AND RE-SUBMIT AS AN AMENDMENT TO THE IRB.

Concurrent Research Studies

Will subjects in this study participate in or be recruited from other studies?

Yes

Describe concurrent research involvement

Screening for this study will be covered by the Substance Treatment and Research Service (STARS) umbrella screening protocol #6582R (PI: [name]). Trained research assistants and administrative assistants under the supervision of the principal investigator conduct the initial phone screening. Under protocol #6582R, patients who contact STARS interested in research trial participation are informed that they will be asked questions of a personal nature and asked to provide verbal consent for such questions. A "phone screen" form is completed by the phone screener, which asks basic demographic information, contact information (for scheduling purposes) and description of substance use to determine whether an in-person evaluation appointment is appropriate. Individuals are also informed that if they make an initial screening appointment this "phone screen" information will be forwarded to the clinician to facilitate the first meeting.

Inclusion/Exclusion Criteria

Name the subject group/sub sample

Adults with OUD

Create or insert table to describe the inclusion criteria and methods to ascertain them

1. Individuals between the ages of 18-65	1. legal identification
2. Voluntarily seeking treatment for opioid use	2. self-report
3. Meets current DSM-5 criteria for OUD as a primary diagnosis, with at least moderate severity	3. clinical interviews; MINI assessment
4. Test positive for HPSO use	4. urine toxicology
5. Able to provide informed consent and comply with study procedures	5. clinical assessment, MMSE (individuals over 60 years old)

Create or insert table to describe the exclusion criteria and methods to ascertain them

1. Meets DSM-5 criteria for substance use disorder other than opioid as the primary diagnosis	1. clinical interviews
2. Having a comorbid psychiatric diagnosis that might interfere with participation or make participation hazardous, such as an active psychotic disorder or current suicide risk	2. clinical interviews
3. Methadone maintenance treatment	3. self-report; urine toxicology
4. Buprenorphine maintenance treatment	4. self-report; urine toxicology
5. Known history of allergy, intolerance, or hypersensitivity to candidate medication (buprenorphine)	5. clinical assessment,

6. Pregnancy, lactation, or failure to use adequate contraceptive methods in female patients; male participants are required to use adequate forms of birth control as the exposure to Sublocade on sperm and subsequent fetal development are not known.	self-report
7. Unstable medical conditions, which might make participation hazardous such as uncontrolled hypertension (blood pressure >150/100), acute hepatitis, uncontrolled diabetes, or elevated liver function tests (AST and ALT >3 times the upper limit of normal	6. serum pregnancy test, self-report
8. Legally mandated to substance use disorder treatment	7. clinical assessment, vital signs, laboratory tests
9. Current physiological dependence on alcohol or sedative-hypnotics that would require a medically supervised detoxification-other substance use diagnoses are not exclusionary	8. self-report
10. Individuals, who in the clinicians judgment, have a history of failed trial of buprenorphine or sublocade (e.g. history of severe opioid intoxication or overdoses despite adequate adherence to buprenorphine or sublocade), or other features of the history that strongly suggest the patient is not a good candidate for outpatient treatment with buprenorphine.	9. clinical assessment
	10. clinical assessment

Waiver of Consent/Authorization

Indicate if you are requesting any of the following consent waivers

Waiver of consent for use of records that include protected health information (a HIPAA waiver of Authorization)

No

Waiver or alteration of consent

No

Waiver of documentation of consent

No

Waiver of parental consent

No

Consent Procedures

Is eligibility screening for this study conducted under a different IRB protocol?

Yes

Indicate NYSPI IRB #

6582R

Describe Study Consent Procedures

Screening for this study will be covered by the Substance Treatment and Research Service (STARS)umbrella screening protocol #6582R (PI: [name]). Trained research assistants and administrative assistants under the supervision of the principal investigator conduct the initial phone

screening. Under protocol #6582R, patients who contact STARS interested in research trial participation are informed that they will be asked questions of a personal nature and asked to provide verbal consent for such questions. A "phone screen" form is completed by the phone screener, which asks basic demographic information, contact information (for scheduling purposes) and description of substance use to determine whether an in-person evaluation appointment is appropriate. Individuals are also informed that if they make an initial screening appointment this "phone screen" information will be forwarded to the clinician to facilitate the first meeting.

Indicate which of the following are employed as a part of screening or main study consent procedures

Consent Form

Persons designated to discuss and document consent

Select the names of persons designated to obtain consent/assent

[name]
[name], MD
[name], MD
[name]
[name]
[name], MD
[name], MD
[name], MD
[name], MD
[name], MD
[name]
[name], MD
[name]

Type in the name(s) not found in the above list

Study Procedures

Describe the procedures required for this study

Screening and Diagnosis: Uniform screening procedures will be used. A standardized telephone screen is followed by an appointment for those who meet general study criteria. No identifying information is recorded until the subject completes the study explanation and consent process; evaluation follows consent using standardized measures. Common, standardized intake and evaluation training will be conducted for all procedures and instruments. Points at which assessments will be made are listed in Table 1. Data collected will be entered or uploaded and maintained in the clinical trials secure electronic database and coded with a unique identifier assigned to each participant. Hospital charts, and Departmental, HIPPA-compliant Research Subject Registration System (KISMER) will, however, contain participants' names.

Eligibility Determination via Physical Examination and Psychiatric Evaluation: Review of history, physical, and laboratory evaluations and the medical-psychiatric evaluation note lead to final determination

of eligibility will be done by the study psychiatrist trained on the protocol.

The MINI International Neuropsychiatric Interview (MINI): will be performed during screening as part of a complete psychiatric diagnostic assessment.

Medical Screening and Evaluation: Medical examination and laboratory work will follow consent. ECGs, blood draws, and urinalyses will be obtained by a lab technician. All tests are conducted using accepted clinical techniques and samples (e.g. bloods) are collected using universal precautions. Pregnancy tests will be conducted for women. A Health Survey will be conducted with special attention devoted to cardiovascular function. A cardiologist is available for STARS participants and will review any abnormal ECGs, and determine whether or not a patient can be safely enrolled in the trial.

Physiological Measures:

- *Medical History and Physical Exam:* A comprehensive medical history and physical examination will be performed during the screening process.
- *Pregnancy Testing:* Serum pregnancy testing will be performed on all females during screening and urine pregnancy tests will be performed at baseline and weeks 4, 8, and 12
- *Serum laboratory examination:* Complete blood count, electrolyte, and liver function tests will be performed during the screening process and follow up at weeks 4, 8, and 12
- *Urinalysis:* Laboratory urinalysis (glucose, protein, ketones, pH, specific gravity, and microscopic analysis) will be performed during the screening process and follow up at weeks 4, 8, and 12
- *Urine Toxicology:* Urine samples will be collected during screening and a full urine toxicology will be tested and at each study visit during the trial. Participants will provide urine twice weekly
- *Electrocardiogram (ECG):* will be completed at baseline
- *Vital Signs and weight/BMI:* Temperature, pulse, blood pressure, and weight with calculated BMI will be measured at each visit for data collection and safety monitoring purposes.

Medication and rationale:

Study Days 1-3: Buprenorphine induction: Study procedures will begin with all participants being inducted onto BSL. For buprenorphine to be safely administered, participants must be in withdrawal from opioids. Individuals will be instructed to abstain from opioids starting at consent and begin buprenorphine medication the day after consent. The day after consent, patients will return to the STARS clinic and be administered a Clinical Opiate Withdrawal Scale (COWS). If found to be in mild withdrawal (COWS score > 6), participants will be started on buprenorphine 2 mg followed by further doses of buprenorphine up to 8 mg on day 1. Because HPSO use may lead to a delayed onset of opioid withdrawal syndrome, the first day that buprenorphine is administered may not be up to three days after a participant's last opioid use.

Whichever day the first dose of BSL is administered will be considered the first day of the induction. The buprenorphine dose will be advanced to a target dose of 24 mg per day on a fixed-flexible schedule, with stabilization at a lower dose if the patient does not tolerate side effects at higher doses. Adequate dosing of buprenorphine is important to its effectiveness, and 16 mg to 24 mg per day is considered the target according to most guidelines.

COMFORT MEDICATIONS: Participants will be given comfort medications to help manage their withdrawal for the first two weeks of the treatment study as needed. Comfort medications prescribed will be

clonidine, clonazepam, prochlorperazine, and zolpidem. Participants will be told that medications may cause some side effects such as sleepiness, lowered blood pressure (which may produce dizziness or a tendency to feel faint), or upset stomach. Participants will be instructed that they should use caution when driving a vehicle or operating appliances or machinery during this time.

Study Day 4: Participants will receive BXR under open-label conditions.

Maintenance Buprenorphine Dosing with BXR treatment: After successful induction onto sublingual buprenorphine, participants will receive BXR (Sublocade) 300 mg subcutaneous injection as per FDA—approved prescribing instructions. The second injection of Sublocade 300 mg will be administered 28 days later. The third injection will occur 28 days subsequent to the second injection at a dose of 100 mg.

Assessment of Side Effects and Medication Compliance: The research nurse and psychiatrist will query about side effects related to the study medication. Reported side effects and other treatment emergent events since the past visit will be recorded; additionally, the severity of the side effect/treatment emergent event, the action taken, and the continuation or resolution of the side effect/treatment emergent event will be documented.

Ongoing assessments: Participants will be asked to provide urine at each visit. They will be asked to complete self-report forms weekly throughout the treatment trial. At each visit, the research staff will monitor vital signs (heart rate and blood pressure) and inquire about medication-related side effects. The Side Effect Questionnaire consists of 2 parts: 1) self-reported side effects obtained by the nurse using an open format and 2) a checklist of symptoms rated from absent to severe, incorporating the major organ systems (e.g., gastrointestinal, neurological, cardiovascular). Serum laboratory and urinalysis will be repeated at weeks 4 and 8 of the trial. Patients may be removed from the study if they repeatedly miss study visits.

Medication Preparation and Dispensing: The New York State Psychiatric Institute Pharmacy is a dedicated, specialized facility that prepares medication for clinical trials including our ongoing STARS trials. STARS has worked exclusively with NYSPI pharmacy on ordering, preparing and dispensing medications to participants. There are a standard set of procedures with regards to this process. First medications are ordered from the pharmacy for each individual participant the week they will be dispensed. The medications provided from the NYSPI pharmacy are only from current, non-expired medication sources. The NYSPI pharmacy provides labeling on all medication bottles or kits that includes the relevant medication, study, participant, and expiration information. Before medication is dispensed to any participant, there is a standard medication dispensation checklist for quality assurance, which requires the study physician and one other staff member to confirm medication name, dosage, quantity, directions/frequency of administration, participant ID, study week, and expiration date. This is reviewed with the participant.

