Risks of buprenorphine (BXR and BSL): Addiction, abuse, and misuse are important risks of buprenorphine: Buprenorphine can be abused in a manner similar to other opioids. Life-threatening respiratory depression and death have occurred in association with buprenorphine. There is a potential danger of self-administration of benzodiazepines or other CNS depressants while under treatment with buprenorphine. There is a risk of opioid withdrawal with abrupt discontinuation: Buprenorphine treatment is associated with a risk of hepatitis. Adverse reactions commonly associated with buprenorphine are constipation, headache, nausea, vomiting, increased hepatic enzymes, and fatigue. There is an increased risk of opioid withdrawal symptoms if the medication is initiated too soon after last opioid dose. Buprenorphine has a risk of opioid related side effects--e.g. nausea, constipation, sedation, respiratory depression (particularly when combined with alcohol or other sedating drugs); worsening of opioid use disorder if the medication does not prove effective or is discontinued by the patient, including functional impairment as well as risk of death from drug overdose.

Risk associated with the combination of buprenorphine and other opioids: There is also the possibility of unexpected reaction if patient's in the study use street opioids or other illicit drugs along with buprenorphine. This risk will be mitigated through weekly medical follow-up with patients throughout the study at medication management sessions which will include a formal assessment for adverse events at each medication management visit. Should unexpected adverse events occur, the study physician will use clinical judgement and shared decision making with the patient to determine the best course of action including lowering or discontinuing buprenorphine.

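### As-needed clonazepam and zolpidem are permitted alongside buprenorphine with no exception for eligible participants who have a secondary alcohol or sedative use disorder, and neither vital-sign list in the protocol text has a respiratory measure

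*Protocol*

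**What the plan says.** Under Study Procedures, the paragraph on comfort medications says "Participants will be given comfort medications to help manage their withdrawal for the first two weeks of the treatment study as needed". The drugs are "clonidine, clonazepam, prochlorperazine, and zolpidem". No dose, quantity or excepted group is stated. The advice to participants covers sleepiness, low blood pressure, stomach upset, and care with driving and machinery.

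Two eligibility criteria bear on who may receive these drugs. Exclusion 1 reads "Meets DSM-5 criteria for substance use disorder other than opioid as the primary diagnosis". Exclusion 9 reads "Current physiological dependence on alcohol or sedative-hypnotics that would require a medically supervised detoxification-other substance use diagnoses are not exclusionary".

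Visit monitoring is described twice. Physiological Measures says "Temperature, pulse, blood pressure, and weight with calculated BMI will be measured at each visit for data collection and safety monitoring purposes". Ongoing assessments says that "the research staff will monitor vital signs (heart rate and blood pressure) and inquire about medication-related side effects". The section on minimizing medication risks repeats that vital signs are taken at each visit and does not list them.

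The risk section for both buprenorphine formulations states that "Life-threatening respiratory depression and death have occurred in association with buprenorphine". It adds that alcohol or other sedating drugs increase the risk of respiratory depression, and that taking benzodiazepines or other CNS depressants during treatment is dangerous. It does not connect either warning to the clonazepam and zolpidem that the study itself makes available.

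**The concern.** The protocol deliberately keeps eligible some people with an alcohol or sedative problem. It names the combination of buprenorphine with alcohol or sedatives as a respiratory hazard. It then allows a benzodiazepine and a hypnotic to be given with buprenorphine for two weeks without saying that this group should be treated differently. All participants test positive for high-potency synthetic opioids at entry, and the protocol says that overdose risk from these remains especially high even on medication.

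What is at stake is participant safety in the first two weeks, and what the study would be able to record. As the text stands, the prescriber has no written criterion for the subgroup, and the vital signs listed for safety monitoring would not register the harm that the protocol itself calls life-threatening.

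**Working it through.** The plan gives no figure to reproduce. The check sets the sections side by side and adds two counts.

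1. **Time overlap.** Take Day 1 as the first sublingual dose, so the comfort-medication window is Days 1 to 14. Sublingual induction occupies Days 1 to 3 and the 300 mg injection is given on Day 4. Overlap with the injection is 14 − 4 + 1 = 11 of 14 days. Adding the 3 induction days gives 3 + 11 = 14 of 14 days with some form of buprenorphine. This counts days on which the two drugs are permitted, not days on which they are taken.

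2. **Eligibility.** Exclusion 1 removes another substance use disorder only when it is primary. Exclusion 9 removes alcohol or sedative dependence only when it would need supervised detoxification, and expressly keeps other substance use diagnoses. A person whose primary diagnosis is opioid use disorder, with a secondary alcohol or sedative use disorder below that threshold, passes both. No other listed criterion excludes that diagnosis as such.

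3. **Respiratory items in the listed vital signs.** Physiological Measures lists temperature, pulse, blood pressure and weight/BMI: none is respiratory. Ongoing assessments lists heart rate and blood pressure: none is respiratory.

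4. **Existing safeguards, put to two questions.**

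| Safeguard in the protocol | Withholds the two drugs from this subgroup? | Records a respiratory value? |
|---|---|---|
| Dispensing checklist: physician and second staff member confirm drug, dose and quantity | No; the text sets no limit or contraindication to check against | No |
| Physician assessment for adverse effects of buprenorphine | No; the listed actions concern study medication or withdrawal from the study | Not specified |
| Monitoring for intoxication and medication misuse | No | Not specified |
| MINI and psychiatric evaluation at screening | No; would identify the subgroup | No |
| Timeline Follow-back of alcohol and other substances | No; would show use | No |
| Weekly session with the research psychiatrist | No; gives an occasion to decide | Not specified |
| Exclusion 10 (poor candidate for outpatient buprenorphine, by clinical judgment) | No; it removes a person from the trial and sets no rule for those enrolled | No |

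5. **Visits at which a respiratory measure could be added.** The protocol supports three counts for the two-week window. Urine Drug Testing under Blood and other Biological Samples has daily visits in week 1, then two a week: 7 + 2 = 9. The payment cap implies 270 / 10 = 27 visits, and 27 − 11 × 2 = 5 in week 1, so 5 + 2 = 7. Twice weekly throughout gives 2 + 2 = 4. These counts size the cost of the fix. They are not three separate pieces of evidence; the single finding is that the two lists lack the item.

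**The case against.** The strongest reply is that this is ordinary prescribing. The drugs are prescribed as needed, so a physician chooses among four and may give neither sedative. Dose and quantity are confirmed for each participant before dispensing. The screening interview would tell the prescriber who has an alcohol or sedative disorder, the Timeline Follow-back tracks use, a psychiatrist sees each participant weekly, and exclusion 10 lets a clinician turn away a poor candidate.

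Much of this stands. A reader might infer that the plan directs clonazepam and zolpidem to everyone, or to the participants at highest risk. It does not: it permits supply and leaves the choice to the prescriber. Nor is the subgroup unmanaged. What remains is narrower. Every safeguard depends on individual judgment, and none states that these two drugs should be withheld from a group that the criteria knowingly admit.

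A second reply concerns monitoring. The protocol refers to a table of assessments for full detail, and that table is not in the file. The two vital-sign lists also differ from each other, so at least one is incomplete. A reader might infer that respiration is not monitored at all. The documents do not support that, because physicians assess adverse effects of buprenorphine at clinic visits and the table may list more. A spot reading in clinic would also miss sedation at home. This weakens the monitoring part and leaves the part about the subgroup intact.

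A third reply is that restricting comfort drugs could cost retention. The SAP's primary outcome is the proportion successfully inducted. If all ten participants are in the denominator, one extra failure moves it by 1/10, or 10 percentage points. That is a real cost, but it is confined to the subgroup and to anyone sedated or intoxicated at a visit, and two comfort drugs remain available to them.

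**Conclusion.** The point holds as a gap in the written plan and a cheap safety improvement. For up to 14 days, 11 of them after the injection, two sedatives may be given with buprenorphine to participants with a secondary alcohol or sedative use disorder, and no rule says otherwise. The vital signs listed in the protocol text include no respiratory measure.

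Two stronger readings are not supported:

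- **A week's home supply.** A reader might take "First medications are ordered from the pharmacy for each individual participant the week they will be dispensed" to mean that seven days of both drugs are held at home. The sentence says when medication is ordered, not how many days are handed over, so no supply figure or percentage reduction follows.
- **A probability of harm.** The documents give no rate of secondary alcohol or sedative use disorder. An assumed rate would show only how likely it is that such a person is enrolled. It would not show that the drugs are prescribed or that harm follows.

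The conclusion rests on Day 1 being the first sublingual dose and on the protocol text alone. If the assessment table already lists respiratory rate or oximetry, the monitoring part falls and the subgroup part stands.

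**What to change.** Make two changes.

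1. In the comfort-medication paragraph, state that clonazepam and zolpidem are not supplied to participants with a current alcohol or sedative use disorder, or to anyone sedated or intoxicated at a visit. Clonidine and prochlorperazine stay available to them, and all four drugs stay available to everyone else.
2. In Physiological Measures, add respiratory rate and pulse oximetry to the visit vital signs for the first two weeks, unless the assessment table already lists them.

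I would not tie resupply to a COWS score above 6. That is the protocol's threshold for starting buprenorphine, and nothing in the documents supports it as a test of whether anxiety or insomnia still needs treatment.

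**Cost.** A few sentences, a pulse oximeter, and about a minute at each of 4 to 9 existing visits per participant: at most 10 × 9 = 90 minutes across the study, with no added visits. The clinical cost is less complete relief of anxiety or insomnia in the subgroup and possibly some added early dropout, the size of which the documents do not allow one to estimate. Clinic readings will not detect events at home, so most of the benefit comes from the first change.
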